5.3. Lifestyle Considerations

1. On study visit days, participants must not administer study intervention until instructed to do so by the investigator or designated study site staff. The study sites need to ensure PROs are completed and clinical assessments performed before dose is administered.
2. On study visit days, showering or bathing is permitted prior to attending the study visit.
3. On study visit days, topical therapies (ie, non-medicated topical therapy and medicated topical therapy, per protocol guidelines as described in [Section 6.5](#)) are not permitted to be applied prior to attending the study visit. Topical therapies are required to be applied after the visit (per protocol guidelines as described in [Section 6.5](#)).
4. The investigator or his or her designee, in consultation with the participant, will confirm that the participant has selected an appropriate method of contraception for the individual participant from the permitted list of contraception methods (see [Appendix 4 Section 10.4](#)) and will confirm that the participant has been instructed in its consistent and correct use. At time points indicated in the [SoA](#), the investigator or designee will inform the participant of the need to use highly effective contraception consistently and correctly and document the conversation and the participant's affirmation in the participant's chart (participants need to affirm their consistent and correct use of at least 1 of the selected methods of contraception). In addition, the investigator or designee will instruct the participant to call immediately if the selected contraception method is discontinued or if pregnancy is known or suspected in the participant or partner.
5. Male participants are not required to use contraception.

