Targeted Physical Exam				X	X	X	X	X	X		X		Refer to Section 8.2.1
Vital Signs	X	X		X	X	X	X	X	X		X	X	Refer to Section 8.2.2 . Temperature does not need to be recorded at the Week 8 visit.
Weight	X												Refer to Section 8.2.1
Height	X	X					X		X				Refer to Section 8.2.1
Chest X-ray	X												Refer to Section 8.2.3 .

Procedure	Screening	Study Intervention Period									EOT / ED Visit	EOS Follow-up Visit (4 weeks after ED/EOT)	Notes			
		1	2	3	4	5	6	7	8	9				10		
		Study Day	D1	D8	D15	D29	D57	D85	D113	D141				D169	D183	D211
		Study Week	WK0	WK1 Call	WK2	WK4	WK8	WK12	WK16	WK20				WK24 Call	WK26	WK30
Visit Window (Days)	-28	0	±1	±1	±2	±3	±3	±3	±3	±3	±3	±3				
ECG (12-lead)	X	X									X	X	Refer to Section 8.2.4 .			
Laboratory Assessments																
Refer to Section 8.2.5 and Appendix 2 for more information on clinical safety laboratory assessments.																
Serum Chemistry and Hematology (including Coagulation Panel and additional sample for infection studies)	X	X		X	X	X	X	X	X		X	X	Refer to Section 8.2.6 for the infection studies and Appendix 2 for all tests			
Lipid Panel		X			X	X		X	X		X	X	8-hour fast required.			
High-sensitivity C-Reactive Protein (hsCRP)	X	X		X	X	X	X	X	X		X	X	This assessment will be blinded after the screening visit.			
Urinalysis	X	X		X	X	X	X	X	X		X	X				
Serum FSH or Pregnancy Test	X												Serum pregnancy testing at screening is required for WOCBP. FSH test to be performed at screening to confirm postmenopausal status in female participants who have been amenorrhoeic for at least 12 months.			
Urine Pregnancy Test (conducted at study site)		X		X	X	X	X	X	X		X	X	This test must be performed prior to dosing with study intervention for WOCBP.			
HIV Testing	X												Will be performed for all participants; those who screen positive will be excluded from the study.			
HBV and HCV Testing	X												Refer to Section 8.2.5.1			
HBV DNA reflex testing	X							X			X		Refer to Appendix 2 and Section 8.2.5.1 .			

Procedure	Screening	Study Intervention Period									EOT / ED Visit	EOS Follow-up Visit (4 weeks after ED/EOT)	Notes			
		Visit	2	3	4	5	6	7	8	9				10		
		Study Day	D1	D8	D15	D29	D57	D85	D113	D141				D169	D183	D211
		Study Week	WK0	WK1 Call	WK2	WK4	WK8	WK12	WK16	WK20				WK24 Call	WK26	WK30
Visit Window (Days)	-28	0	±1	±1	±2	±3	±3	±3	±3	±3	±3	±3				

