Skin Pain NRS		X		X			X	X	X		X		Refer to Section 8.1.6.8
Asthma Control Questionnaire (ACQ)		X					X				X	X	Refer to Section 8.1.6.9 . Given to all participants with a prior diagnosis of asthma.

Procedure	Screening	Study Intervention Period										EOT / ED Visit	EOS Follow-up Visit (4 weeks after ED/EOT)	Notes
		1	2	3	4	5	6	7	8	9	10			
Visit		D1	D8	D15	D29	D57	D85	D113	D141	D169	D183	D211		
Study Day		WK0	WK1 Call	WK2	WK4	WK8	WK12	WK16	WK20	WK24 Call	WK26	WK30		
Study Week														
Visit Window (Days)	-28	0	±1	±1	±2	±3	±3	±3	±3	±3	±3	±3		
Optional Accelerometry														
Accelerometry training/retraining	X	X	X	X			X	X	X		X			Refer to Section 8.1.7
Issue/collect accelerometry devices	X	X		X			X	X	X		X			
Night Time Itch Accelerometry	X-----X	X-----X					X	X	X		X			
Hand Eczema Clinical Assessments														
History, subtype, clinical signs and extent	X													Refer to Section 8.1.8 .
Investigator's global assessment (IGA)	X	X		X	X	X	X	X	X		X	X		
Safety														
C-SSRS	X	X				X	X	X	X		X	X		Refer to Section 8.2.7.1
PHQ-8	X													Refer to Section 8.2.7.2
Serious and non-serious adverse event monitoring	X	X	X	X	X	X	X	X	X	X	X	X		Refer to Appendix 3 .
Contraception Check	X	X	X	X	X	X	X	X	X	X	X	X		Refer to Appendix 4 for contraceptive guidance.
Banked Biospecimens														
Banked Biospecimen for Genetics		X												Required to be collected for all participants (as local regulations and IRBs/ECs allow). Collect a 2 mL blood sample optimized for DNA isolation (Prep D1.5). Refer to Section 8.7.2 .

Procedure	Screening	Study Intervention Period									EOT / ED Visit	EOS Follow-up Visit (4 weeks after ED/EOT)	Notes
		1	2	3	4	5	6	7	8	9			
Visit		D1	D8	D15	D29	D57	D85	D113	D141	D169	D183	D211	
Study Day													
Study Week		WK0	WK1 Call	WK2	WK4	WK8	WK12	WK16	WK20	WK24 Call	WK26	WK30	
Visit Window (Days)	-28	0	±1	±1	±2	±3	±3	±3	±3	±3	±3	±3	
Banked Biospecimens for Biomarkers		X		X									Required to be collected for all participants (as local regulations and IRBs/ECs allow). Collect 4 mL blood sample optimized for biomarkers (Prep B2.5) and isolate serum. Collect a 2.5 mL blood sample optimized for RNA isolation (Prep R1). Refer to Section 8.8.4 .

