5.1. Inclusion Criteria

Participants are eligible to be included in the study only if all of the following criteria apply:
Age

1. Participants must be 18 years of age or older inclusive, at the time of signing the informed consent.

Type of Participant and Disease Characteristics

2. Participants who meet all of the following atopic dermatitis criteria:
 - Clinical diagnosis of chronic atopic dermatitis (also known as atopic eczema) for at least 6 months prior to Day 1 and has confirmed atopic dermatitis at the screening and baseline visits according to Hanifin and Rajka criteria for AD.²¹ Refer to [Appendix 9](#).
 - Documented recent history (within 6 months before the screening visit) of inadequate response to treatment with medicated topical therapy for AD for at least 4 consecutive weeks, or who have required systemic therapies for control of their disease within the past year. NOTE: Medicated topical therapy is defined as a topical product that contains an active pharmaceutical ingredient indicated for the treatment of AD (irrespective of whether it is an over-the-counter [OTC] or prescribed product).
 - Moderate to severe AD (BSA $\geq 10\%$, IGA ≥ 3 , EASI ≥ 16 , and PP-NRS severity score ≥ 4 on the day of the baseline visit).

Sex

3. Male or Female

Contraceptive use by men or women should be consistent with local regulations regarding the methods of contraception for those participating in clinical studies.

a. Male participants:

No contraceptive measures are required.

b. Female participants:

A female participant is eligible to participate if she is not pregnant or breastfeeding, and at least one of the following conditions applies:

- Is not a woman of childbearing potential (WOCBP) (see definitions below in Section 10.4.3)

OR

- Is a WOCBP and using a contraceptive method that is highly effective (with a failure rate of <1% per year), as described below, during the intervention period and for at least 28 days after the last dose of study intervention, which corresponds to the time needed to eliminate any reproductive safety risk of the study intervention(s). If a highly effective method that is user dependent is chosen, *a second effective method of contraception, as described below, must also be used*. The investigator should evaluate the effectiveness of the contraceptive method in relationship to the first dose of study intervention.

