10.4.4. Contraception Methods

Contraceptive use by men or women should be consistent with local availability/regulations regarding the use of contraceptive methods for those participating in clinical trials.

1. Implantable progestogen-only hormone contraception associated with inhibition of ovulation.
2. Intrauterine device.
3. Intrauterine hormone-releasing system.
4. Bilateral tubal occlusion.
5. Vasectomized partner:
 - Vasectomized partner is a highly effective contraceptive method provided that the partner is the sole sexual partner of the woman of childbearing potential and the absence of sperm has been confirmed. If not, an additional highly effective method of contraception should be used. The spermatogenesis cycle is approximately 90 days.

6. Combined (estrogen- and progestogen-containing) hormonal contraception associated with inhibition of ovulation:
 - Oral;
 - Intravaginal;
 - Transdermal;
 - Injectable.
7. Progestogen-only hormone contraception associated with inhibition of ovulation:
 - Oral;
 - Injectable.
8. Sexual abstinence:
 - Sexual abstinence is considered a highly effective method only if defined as refraining from heterosexual intercourse during the entire period of risk associated with the study intervention. The reliability of sexual abstinence needs to be evaluated in relation to the duration of the study and the preferred and usual lifestyle of the participant.

In addition, one of the following effective barrier methods must also be used when option 6 or 7 are chosen above:

- Male or female condom with or without spermicide;
- Cervical cap, diaphragm, or sponge with spermicide;
- A combination of male condom with either cervical cap, diaphragm, or sponge with spermicide (double-barrier methods).

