10.13.1. Telehealth visits

In the event that in-clinic study visits cannot be conducted, every effort should be made to follow up on the safety of study participants at scheduled visits per the Schedule of Activities or unscheduled visits. Telehealth visits may be used to continue to assess participant safety and collect data points. Telehealth includes the exchange of healthcare information and services via telecommunication technologies (e.g., audio, video, video-conferencing software) remotely, allowing the participant and the investigator to communicate on aspects of clinical care, including medical advice, reminders, education, and safety monitoring. The following assessments must be performed during a telehealth visit:

- Review and record study intervention(s), including compliance and missed doses.
- Review and record any AEs and SAEs since the last contact. Refer to Section 8.3.
- Review and record any new concomitant medications or changes in concomitant medications since the last contact.
- Review eDiary for completion, including the participant's understanding of the daily completion requirements;
- Review accelerometry and arrange for return of used devices and sending of new devices, if applicable.
- Complete contraceptive check and results of pregnancy testing. Confirm that the participant is adhering to the contraception method(s) required in the protocol. Refer to [Appendix 4](#) regarding pregnancy tests.
- Administer the C-SSRS and follow-up as necessary per protocol Section [8.2.7](#).

Study participants must be reminded to promptly notify site staff about any change in their health status.

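### The contraception affirmation in Protocol Section 5.3 can be met with one method, although women on option 6 or 7 are required to use two

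*Protocol*

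**What the plan says.** Section 5.3, item 4, of the Protocol governs the contraception check after a method has been selected. At the Schedule of Activities time points, staff are to "inform the participant of the need to use highly effective contraception consistently and correctly" and to chart both the conversation and her affirmation. The parenthesis that follows states what the affirmation must contain: "participants need to affirm their consistent and correct use of at least 1 of the selected methods of contraception". The item closes by saying that staff "will instruct the participant to call immediately if the selected contraception method is discontinued".

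The underlying requirement is set elsewhere. Inclusion criterion 3b (Section 5.1), repeated in Section 10.4.2, says that if the chosen highly effective method is user dependent, "a second effective method of contraception, as described below, must also be used". It applies throughout the intervention period and for at least 28 days after the last dose. Section 10.4.4 supplies the detail: "In addition, one of the following effective barrier methods must also be used when option 6 or 7 are chosen above". Option 6 is combined hormonal contraception; option 7 is progestogen-only oral or injectable contraception.

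Two other places describe the same check. The note on the Contraception Check row of the Schedule of Activities (Section 1.3) reads "Refer to Appendix 4 for contraceptive guidance". Sections 10.13.1 and 10.13.2, on telehealth and home visits, both say: "Confirm that the participant is adhering to the contraception method(s) required in the protocol".

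**The concern.** For women on option 6 or 7, the standard written for the affirmation is lower than the standard they are required to meet. A participant who has let one of her two methods lapse can give an affirmation that satisfies item 4, and the chart will show a completed check.

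What is at stake is avoidance of pregnancy during exposure. Criterion 3b ties its contraception requirement to reproductive risk from the study interventions, and Section 10.4.1 refers to developmental toxicity seen in nonclinical studies. The affirmation is the chart entry on current contraceptive use, so it ought to test the rule the protocol imposes. Nothing in the efficacy analyses, power or error control depends on it.

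**Working it through.** There is no stated figure to reproduce. The check compares the texts and then counts visits.

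**Methods required against methods affirmed**

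| Method chosen (Section 10.4.4) | Required | Minimum affirmed under 5.3, item 4 |
|---|---|---|
| Options 1 to 4 and 8 | 1 (no barrier rule) | 1 |
| Option 5, vasectomized partner | 1, or an additional highly effective method if the stated conditions on the partner are not met | 1 |
| Option 6, combined hormonal | 2 (hormonal and barrier) | 1 |
| Option 7, progestogen-only oral or injectable | 2 (hormonal and barrier) | 1 |

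Criterion 3b does not itself name options 6 and 7 or barriers. It speaks of a user-dependent method and a second effective method, and Appendix 4 fills in the rest. The mismatch appears when the two are read together.

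For options 6 and 7, two kinds of lapse can pass:

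1. The hormonal method is stopped and the barrier kept. On the literal wording she still uses one of her selected methods.
2. The hormonal method is kept and the barrier dropped. She meets the wording more comfortably still.

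**Checks at which it matters** (counts from the Schedule of Activities)

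- Contraception check: 12 columns (screening, Day 1, Weeks 1, 2, 4, 8, 12, 16, 20, 24, 26 and 30).
- Inclusion and exclusion review: 2 columns (screening and Day 1).
- Checks after Day 1: 12 − 2 = 10.
- Urine pregnancy test: 9 columns (Day 1, Weeks 2, 4, 8, 12, 16, 20, 26 and 30), so 9 − 1 = 8 after Day 1.
- Checks after Day 1 with no scheduled test: 10 − 8 = 2 (the Week 1 and Week 24 calls).
- Review of prior and concomitant medication: all 12 columns, hence all 10 after Day 1.

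Ten is a maximum per participant. Those who enter the extension study have no Week 30 visit, which leaves 10 − 1 = 9 checks, 8 − 1 = 7 of them with a test.

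**Whether another procedure closes the gap**

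- Medication review may reveal a stopped hormonal drug, but it is not a check on condom or diaphragm use.
- Pregnancy tests detect a failure after the event; they do not verify adherence.
- The instruction to call relies on self-report and refers to the selected method in the singular.
- The Appendix 13 checks do ask about the required method or methods, but only at remote visits during public emergencies. Read literally, a telehealth visit applies a stricter check than the affirmation described in item 4.

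**The case against.** The best counter-argument is that item 4 should be read as a whole. Its sentence begins with the need for highly effective contraception. In Appendix 4 the barriers are described only as effective, and they sit outside the numbered list as an add-on to options 6 and 7. A barrier-only answer therefore fits badly with the rest of the sentence, and a sensible site would not accept it. That has force against the first kind of lapse. It does not help with the second: if the single affirmed method is taken to be the hormonal one, the mandatory barrier goes unaffirmed. On either reading one required method is missed.

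The second argument is that the binding rule is unaffected. Criterion 3b runs through treatment and for at least 28 days afterwards, item 4 refers to Appendix 4 for the choice of method, and the Schedule of Activities row sends staff there too. This stands. No woman is permitted to use one method where two are required, and the defect is confined to what she is asked to affirm.

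There are further safeguards. Section 8.2.8 adds pregnancy testing when a menstrual period is missed and bars further progress until pregnancy is ruled out. The Appendix 13 checks apply for the duration of the COVID-19 pandemic, and the United Kingdom has a 12-week call on adherence to the contraception guidelines (Section 10.12.3). These reduce the consequence and support a low rating. At routine site visits and calls, none of them asks her to confirm that both methods are in use.

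**Conclusion.** The concern holds as a minor internal inconsistency on a safety procedure. For women on option 6 or 7, item 4 accepts affirmation of one method where criterion 3b and Appendix 4 require two. The looser wording applies at up to 10 checks per participant after Day 1, two of which have no scheduled pregnancy test.

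The conclusion rests on reading the parenthesis as the definition of what must be affirmed, and on reading criterion 3b together with Section 10.4.4. It does not depend on whether a site would accept a barrier-only answer. The documents do not say how many participants are of childbearing potential or will choose option 6 or 7, so the number affected cannot be estimated.

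**What to change.** Replace the parenthesis in Section 5.3, item 4, with wording such as:

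*each participant affirms that she is currently using, consistently and correctly, every contraceptive method Appendix 4 requires for her; where option 6 or 7 is selected, this means both the hormonal and the barrier method.*

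This covers both kinds of lapse, and also the option 5 case in which an additional method is needed. It brings item 4 into line with the Schedule of Activities note and with Appendix 13. Any source-document or CRF prompt for the contraception check should be worded to match; those forms are not among the documents, so whether they need changing is not known.

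The cost is one phrase in the protocol and any matching prompt. No visit, test or procedure is added.

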5.3.1. Meals and Dietary Restrictions

On study visit days as per the [Schedule of Activities](#), participants must comply with fasting requirements for at least 8 hours prior to the visit. Water and permitted non-study medications are allowed ([Section 6.5.1](#)).

If the participant experiences nausea, consideration should be given to administering the oral study intervention with food.

5.3.2. Caffeine, Alcohol, and Tobacco

Participants will abstain from using tobacco products or ingesting caffeine- or xanthine-containing products (eg, coffee, tea, cola drinks, and chocolate) for at least 30 minutes before pulse rate and blood pressure measurements.

5.3.3. Vaccine and Exposure to Infections Guidelines

5.3.3.1. Participant Specific Recommendations

It is recommended that all participants should be up-to-date with respect to standard-of-care vaccinations (as defined by their country health ministry or AD guidelines). Vaccination of participants with live components is prohibited within the 6 weeks prior to first dose of study intervention.

5.3.3.2. Guidance Regarding Household Contact Vaccine-Related Exposure

Current routine household contact with children and others who have been vaccinated with live vaccine components may pose a risk during treatment and for 6 weeks following completion of the study. Some of these vaccines include varicella (“chickenpox”) vaccine, oral polio vaccine, and the inhaled flu vaccine. Following vaccination with live component vaccines, the virus may be shed in bodily fluids, including stool, and there is a potential risk that the virus may be transmitted. General guidelines for immunosuppressed participants suggest that exposure (through routine contact) should be avoided following vaccination (of others) with these vaccines for the stated time period:

- a. Varicella or attenuated typhoid fever vaccination for 4 weeks following vaccination.
- b. Oral polio vaccination for 6 weeks following vaccination.
- c. Attenuated rotavirus vaccine for 10 days following vaccination.
- d. FluMist[®] (inhaled flu vaccine) for 1 week following vaccination.
- e. Measles, Mumps and Rubella vaccine for 4 weeks following vaccination.
- f. Yellow fever vaccine for 4 weeks following vaccination.

Participants should avoid exposure to vaccinated or infected persons and contact the investigator promptly should they develop signs or symptoms of infections.

5.3.4. Surgery

During the study, no elective surgery should occur without first consulting with the Pfizer clinician or designee. Preferably, elective surgery should occur before the study or be delayed until study participation is completed.

The Pfizer clinician or designee should be notified if a participant requires surgery (including dental surgery) during the study to determine whether the participant should discontinue from

the study and/or discontinue study intervention prior to the surgical procedure. In general, planned surgical procedures should not be performed unless the study intervention has been discontinued for at least 28 days (unless otherwise advised by the Pfizer clinician or designee). The Pfizer clinician or designee should be notified as soon as possible if a participant undergoes a surgical procedure without first informing the study staff.

5.4. Screen Failures

Screen failures are defined as participants who consent to participate in the clinical study but are not subsequently randomly assigned to study intervention/entered in the study. A minimal set of screen failure information is required to ensure transparent reporting of screen failure participants to meet the Consolidated Standards of Reporting Trials (CONSORT) publishing requirements and to respond to queries from regulatory authorities. Minimal information includes demography, screen failure details, eligibility criteria, and any serious adverse event (SAE).

Individuals who do not meet the criterion for participation in this study (screen failure) may be rescreened once if they fail the screening evaluation for reasons related to incidental transitory conditions. Individuals for whom screen failure is related to failing the disease severity (including extent of disease) inclusion criteria and who subsequently experience worsening AD, which in the investigator's judgement would make them eligible for participation, may be considered for re-screening. Such cases should be discussed with the Pfizer Medical Monitor (or designee) to determine if re-screening is appropriate.

